3. STUDY DESIGN

Type of study: Randomised controlled trial

Duration: 4 week trial with 1 week pre-randomisation assessment

FIRST1D protocol v1.7 23.2.18
IRAS ID: 237129

Number and type of subjects:

16 participants with type 1 diabetes referred for CSII, randomised 1:1 to circadian insulin infusion rates or flat rates.

Recruitment will be undertaken in the T1DM clinics at Imperial College Healthcare NHS Trust. Participant information sheets will be given to potential subjects who have been assessed and screened for insulin pump therapy, either in person in clinic, or via post with a participant invitation letter. After a minimum of 24 hours and following any questions, informed consent will be taken.

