3.1 STUDY OUTCOME MEASURES**Primary outcome:**

- Absolute change in insulin basal rate over 24 hours after 3 rounds of basal rate testing (calculated by the sum of absolute changes for each 1 hour block compared with baseline)

Secondary outcomes:

- Healthcare professional time spent with subject
- Mean sensor glucose from continuous glucose monitoring after 3 rounds of basal rate testing
- Mean sensor glucose from continuous glucose monitoring after 1 round of basal rate testing
- Number of healthcare professional contacts
- CGM outcomes
 - %time in hypoglycaemia (<2.8mmol/L)
 - %time in hypoglycaemia (<3.3mmol/L)
 - %time in hypoglycaemia (<3.9mmol/L)
 - %time in target (3.9-10mmol/L)
 - %time spent in hyperglycaemia (>10mmol/L)
 - Measures of glycaemic variability
 - Mean glucose
 - Glucose SD
- Severe hypoglycaemia
- Insulin outcomes
 - Number of insulin time blocks changed
 - Number of insulin basal rate changes
 - Change to total daily insulin dose
- Basal insulin:bolus insulin ratio
- Healthcare professional qualitative feedback

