4.2 INCLUSION CRITERIA

- Adults ≥ 18 years of age
- Diagnosis of T1DM for > 1 year
- On MDI with decision made to commence CSII
- Structured education in previous 3 years
- HbA1c ≤ 75 mmol/mol (9%)
- Stimulated c-peptide < 200 pmol/L
- No severe hypoglycaemia (defined as needing 3rd party assistance) in previous year

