7. STATISTICS AND DATA ANALYSIS

This is a single site randomised study with an intervention group and a control group. The primary outcome is absolute change in insulin basal rate over 24 hours after 3 rounds of basal rate testing (calculated by the sum of absolute changes for each 1 hour block compared with baseline). This is a pilot study and will demonstrate the effect size of circadian basal rates. A post hoc power calculation will be performed.

The sample size is comparable to other diabetes technology studies, and is a realistic number for recruitment in the time period. In 2015-2016 47 people with type 1 diabetes commenced insulin pump therapy at Imperial College.

Data will be entered onto a database with restricted fields by the research team and, following data checking and cleaning, analysis will be conducted using Stata statistical software. Analysis will be conducted by [name], [name] (Reader in Human Metabolism) and the Imperial College Statistics Service. The primary and secondary outcomes will be analysed by intention to treat analysis. The difference in basal rate change between the two groups at the endpoint will be assessed by a two-tailed independent t test. Secondary outcomes will be assessed by independent t test or, if data are non-parametric, a Mann-Whitney U test. Missing data will be minimised by reducing manual data entry, using technology to collect glucose data, and by carefully supporting participants. Where present, missing data will be handled by full analysis of the available data only.

Data and all appropriate documentation will be stored for a minimum of 10 years after the completion of the study, including the follow-up period. Anonymised data will be kept on university password-protected computers in a locked room. Access is only available to the clinical research team. The identifier codes will be kept on password-protected NHS computers. The anonymised data includes CGM data, food and exercise diaries and blood test.

The paper copies of the consent forms and questionnaires will be kept in a specifically labelled FIRST1D file in a locked cupboard in the diabetes research office

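### Severe hypoglycaemia falls under a t test or Mann-Whitney rule that gives undefined or misleading output, and no interval, for a sparse event in 8 per arm

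*Combined protocol and SAP*

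**What the plan says.** Section 3.1 lists "Severe hypoglycaemia" among the secondary outcomes. It does not say whether the outcome is participants affected (yes or no) or number of episodes. Section 7 then states a single rule for the whole list: "Secondary outcomes will be assessed by independent t test or, if data are non-parametric, a Mann-Whitney U test". No section gives an exact test, a count model or descriptive reporting for this outcome.

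Three other statements bear on how many events to expect:

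- Section 3, on size: "16 participants with type 1 diabetes referred for CSII, randomised 1:1 to circadian insulin infusion rates or flat rates".
- Section 3, on length: "Duration: 4 week trial with 1 week pre-randomisation assessment". Section 6 places the last visit at around day 32 of pump therapy.
- Section 4.2, on entry: "No severe hypoglycaemia (defined as needing 3rd party assistance) in previous year".

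The plan gives no expected event rate and no significance level. Two-sided testing is stated only for the primary outcome: "The difference in basal rate change between the two groups at the endpoint will be assessed by a two-tailed independent t test".

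**The concern.** Severe hypoglycaemia is a yes/no or count outcome, and here it will probably be zero for most or all participants. A comparison of means or ranks summarises such data poorly. The method is stated rather than left open, so an analyst who follows the plan would produce it.

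Two things are at stake. With no events, the planned analysis has no usable result and does not convey how little 8 people per arm can rule out. With a handful of events, the printed p-value can look more suggestive than the randomisation justifies. Section 7 describes the trial as a pilot meant to show an effect size, so an estimate with an honest interval is worth more here than a p-value.

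**Working it through.** **Inputs.** 16 participants allocated 1:1, so n = 8 per arm (section 3). About 28 to 32 days on the pump (sections 3 and 6), so total follow-up is 16 × 28/365 = 1.23 to 16 × 32/365 = 1.40 person-years. Assumed, because the documents do not say: two-sided tests at 0.05, all 16 analysed, and a 2% to 20% risk of at least one episode per participant. The plan states no figure of its own on this point, so there is nothing to reproduce.

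**Step 1: how sparse?** The probability of no event among 16 is (1 − p)^16: 0.72 at p = 2%, 0.44 at 5%, 0.19 at 10%.

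**Step 2: no events.** The pooled variance is 0 and so is the mean difference, so t = 0/0. The tie-corrected Mann-Whitney variance is proportional to (N + 1) − (T³ − T)/[N(N − 1)]. With all N = T = 16 values tied, this is 17 − 4080/240 = 0, so that statistic is also undefined.

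**Step 3: k affected in one arm, none in the other.**

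- Pooled t: t = (k/8)/√(s²/4), where s² is the pooled variance, on 14 df. For k = 3, s² = 0.134 and t = 0.375/0.183 = 2.05.
- Mann-Whitney, normal approximation with tie correction and no continuity correction: z² = (15/16) × Pearson chi-square. For k = 3, z² = (15/16) × 3.692 = 3.46.
- Exact randomisation probability (Fisher), given k affected in total: 2 × C(8,k)/C(16,k). For k = 3, 112/560 = 0.200; for k = 4, 140/1820 = 0.077.

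| Affected | t test | Mann-Whitney | Fisher | Fisher ÷ t | Fisher ÷ MW |
|---|---|---|---|---|---|
| 1 v 0 | 0.334 | 0.317 | 1.000 | 3.0 | 3.2 |
| 2 v 0 | 0.149 | 0.143 | 0.467 | 3.1 | 3.3 |
| 3 v 0 | 0.060 | 0.063 | 0.200 | 3.4 | 3.2 |
| 4 v 0 | 0.019 | 0.025 | 0.077 | 4.0 | 3.0 |

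The first row is the clearest. If exactly one person is affected, the split must be 1 v 0, so the two-sided probability is 1, yet the t test prints 0.33. Counting episodes does not help: one participant with 2, 3 or 5 episodes against none still gives t test 0.334, Mann-Whitney 0.317 and permutation 1.000.

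**Step 4: what an exact interval shows.** For 0/8 the upper 95% limit is 1 − 0.025^(1/8) = 0.369. For 1/8 the exact interval is 0.3% to 52.7%.

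**Step 5: do the planned tests reject too often?** Type I error is the sum, over all pairs (a, b), of Bin(a; 8, p) × Bin(b; 8, p) where the p-value is below 0.05. At p = 5% the main contribution is the 4 v 0 split in either direction: 2 × 70 × 0.05⁴ × 0.95¹² = 0.00047.

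| Event rate | t test | Mann-Whitney | Fisher |
|---|---|---|---|
| 2% | 0.00002 | 0.00002 | <0.00001 |
| 5% | 0.0005 | 0.0005 | 0.00002 |
| 10% | 0.005 | 0.005 | 0.0004 |
| 20% | 0.027 | 0.026 | 0.004 |
| 30% | 0.053 | 0.047 | 0.012 |

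The t test passes 5% only at about a 30% rate, which is not a rare event.

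**The case against.** A reader who sees the table of p-values might infer that the planned tests will produce false safety signals. The documents and the arithmetic do not support that. For a rare event both tests reject far less often than 5%. With three or fewer participants affected, none of the tests falls below 0.05. The first split on which they and Fisher disagree at that level is 4 v 0. Four or more affected among 16 has probability 0.0002 at a 2% rate, 0.007 at 5% and 0.068 at 10%.

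Part of the gap is also Fisher's own conservatism. For 3 v 0, Fisher's mid-p is 0.100 and Barnard's test gives 0.082; for 4 v 0 they give 0.038 and 0.028. Section 7 does not say which Mann-Whitney calculation would be used. An exact version, feasible with 16 people, gives the same p-values as Fisher on these tables (1.000, 0.467, 0.200, 0.077), and mostly-zero data might well be sent to that test rather than to the t test.

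Nor do the documents call this the main safety comparison. It is one item in a long secondary list that also has three CGM hypoglycaemia thresholds, adverse events are recorded separately under section 5, and no decision is tied to its p-value.

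All of that stands. It removes any claim of inflated significance. It does not make the stated rule suitable: the exact version is not specified, the t test remains an option, and neither test yields an interval for the risk in each arm or says whether participants or episodes are counted.

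**Conclusion.** The concern holds as a mismatch between method and outcome, and it is minor. For severe hypoglycaemia the stated rule gives an undefined result when there are no events. With a few events, the t test and the normal-approximation Mann-Whitney test give p-values of about a third to a quarter of the exact randomisation probability. Under either test the reader is not shown that 0/8 leaves a risk of up to 37% open. It does not follow that false positives are inflated: at assumed rates up to 20% the type I error stays below 3%.

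The p-values and exact limits depend only on 8 per arm being analysed. The error rates and the expectation of few events rest on the assumed event rates and a two-sided 0.05 level, neither of which is in the documents. The short follow-up and the entry criterion make low rates plausible but do not fix them.

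**What to change.** In section 7, exempt severe hypoglycaemia from the t test/Mann-Whitney rule. State that, for each arm, the report will give the number of participants with at least one episode and the total number of episodes, with exact 95% confidence intervals for the proportions, and that Fisher's exact test will be used if a test is wanted. This also settles what is being counted.

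The cost is one sentence, with no new data, visits or participants. The small downside is that Fisher's test is conservative at this size, so the intervals, not the p-value, should carry the interpretation.

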8. REGULATORY ISSUES

8.1 ETHICS APPROVAL

The Chief Investigator has obtained approval from the **xxx** Research Ethics Committee and the HRA. The study must be submitted for confirmation of capacity and capability (CCC) at each participating NHS Trust. The study will be conducted in accordance with the recommendations for physicians involved in research on human subjects adopted by the 18th World Medical Assembly, Helsinki 1964 and later revisions.

8.2 CONSENT

Consent to enter the study must be sought from each participant only after a full explanation has been given, an information leaflet offered and time allowed for consideration. Signed participant consent should be obtained. The right of the participant to refuse to participate without giving reasons must be respected. After the participant has entered the study the clinician remains free to give alternative treatment to that specified in the protocol at any stage if he/she feels it is in the participant's best interest, but the reasons for doing so should be recorded. In these cases the participants remain within the study for the purposes of follow-up

and data analysis. All participants are free to withdraw at any time from the protocol treatment without giving reasons and without prejudicing further treatment.

8.3 CONFIDENTIALITY

The Chief Investigator will preserve the confidentiality of participants taking part in the study and is registered under the Data Protection Act.

8.4 INDEMNITY

Imperial College London holds negligent harm and non-negligent harm insurance policies which apply to this study

8.5 SPONSOR

Imperial College London will act as the main Sponsor for this study. Delegated responsibilities will be assigned to the NHS trusts taking part in this study.

8.6 FUNDING

Roche are funding this study. Travel expenses will be provided for participants of the study.

8.7 AUDITS

The study may be subject to inspection and audit by Imperial College London under their remit as sponsor and other regulatory bodies to ensure adherence to GCP and the NHS Research Governance Framework for Health and Social Care (2nd edition).

9. STUDY MANAGEMENT

The day-to-day management of the study will be co-ordinated [name]

10. PUBLICATION POLICY

Data from the study will be analysed then published in peer-reviewed scientific journals and presented at Scientific Conferences. A lay summary of the data will be disseminated to all participants and a summary of results will be publically available.

Appendix 1. Summary of investigations, treatment and assessments

	Usual pre pump assessment and screening appointment	Informed consent appointment	Pre-randomisation	Days post CSII initiation			
				0	7	14	28
Informed consent		X					
Blood tests (Thyroid function tests, coeliac serology, plasma glucose, serum c-peptide)	X						X
HbA1c (blood test)	X						X
GOLD score questionnaire	X						X
Blinded CGM			X	X	X	X	X
Psychosocial questionnaires			X				X
Basal rate testing					X	X	X
Pump download					X	X	X

Appendix 2. Participant information sheet

Appendix 3. Consent form

Appendix 4. GP letter

Appendix 5. Participant invite letter

Appendix 6. Questionnaire to measure awareness of hypoglycaemia (Gold)

Appendix 7. Questionnaire to measure Hypoglycaemia fear (HFS-II)

Appendix 8. Questionnaire to measure general quality of life (WHOQoLBref)

Appendix 9. Questionnaire to measure Diabetes distress (DDS)

Appendix 10. Questionnaire to measure Diabetes QoL (DQOL)
